6.6 Blinding of IMP

This is an open label study with no requirement for blinding.

6.7 Destruction of IMP

Following IMP accountability and written permission from the Sponsor to destroy IMP, documentation of destruction must contain, at a minimum, the following:

- Identity, lot number or subject number;
- Quantity;
- Date of destruction;
- Method of destruction;
- Name and signature of person or company responsible for destruction.

Page 48 of 76

7 Assessment of Safety

The methods for collecting safety data are described below.

7.1 Adverse Events and Laboratory Abnormalities

7.1.1 Clinical Adverse Events

Adverse Event

An *Adverse Event* is any untoward medical occurrence in a subject which does not necessarily have to have a causal relationship with the administration of an IMP. An AE can therefore be any unfavorable and unintended sign, symptom or disease temporally associated with the use of the IMP, whether or not considered related to the medicinal product. Pre-existing conditions that worsen in severity during the course of the study are to be reported as AEs.

All AEs occurring during the clinical study will be reported on the AE page of the eCRF as described in Section 7.3.

The Investigator will assess the severity, causality (relationship to IMP), and seriousness of each AE.

Severity: The severity of AEs will be graded according to the National Cancer Institute Common Terminology Criteria for Adverse Events (CTCAE), version 4.0 or higher. The CTCAE displays Grades 1 through 5 with unique clinical descriptions of severity for each AE based on the general guideline below. Detailed instructions on grading of events by Medical Dictionary for Regulatory Activities (MedDRA) system organ class and lower level term are available online.

- **Grade 1** Mild; asymptomatic or mild symptoms; clinical or diagnostic observations only; intervention not indicated.
- **Grade 2** Moderate; minimal, local or noninvasive intervention indicated; limiting age-appropriate instrumental activities of daily life (e.g., preparing meals, shopping for groceries or clothes, using the telephone, managing money).
- **Grade 3** Severe or medically significant but not immediately life-threatening; hospitalization or prolongation of hospitalization indicated; disabling; limiting self-care activities of daily life (e.g., bathing, dressing and undressing, feeding self, using the toilet, taking medications, and not bedridden).
- **Grade 4** Life-threatening consequences; urgent intervention indicated.
- **Grade 5** Death related to AE.

Causality: AEs will be assessed by the Investigator as not related, unlikely related, possibly related, or related to IMP. Table 3 provides general guidance on the assessment of causality. Assessment of causality should be based on the Investigator's medical judgment and the observed symptoms associated with the event. For data reporting purposes, related AEs will be

Page **49** of **76**

those assessed by the Investigator as possibly related or related to IMP, and unrelated AEs will be those assessed by the Investigator as not related or unlikely related to IMP.

Relationship to IMP	Criteria for Judgment
Related	Reasonable temporal relationship of the clinical event to IMP administration AND cannot be reasonably explained by other factors (such as the subject's clinical state, concomitant therapy, and / or other interventions).
Possibly Related	The temporal relationship of the clinical event to IMP administration makes causal relationship possible but not unlikely AND other drugs, therapeutic interventions or underlying conditions do not provide a sufficient explanation for the observed event.
Unlikely Related	The temporal relationship of the clinical event to IMP administration makes causal relationship unlikely but not impossible AND other drugs, therapeutic interventions or underlying conditions provide a plausible explanation for the observed event.
Not Related	Data are available to clearly identify an alternative cause for the reaction.

Table 3Assessment of Causality

Seriousness: AEs will be classified as serious or non-serious according to the definitions provided below.

Serious Adverse Event

A serious adverse event is any AE that results in any of the following outcomes:

- Death
- Immediately life threatening
- Requires inpatient hospitalization or prolongation of existing hospitalization
- Results in congenital anomaly/birth defect
- Results in a persistent or significant disability or incapacity
- An important medical event that may not result in death, be life threatening, or require hospitalization may be considered an SAE when, based upon appropriate medical judgment, the event may jeopardize the subject and may require medical or surgical intervention to prevent one of the outcomes listed.

All AEs that do not meet any of the criteria for serious, should be regarded as **non-serious adverse events**. Given the severity and life threatening nature of LAL Deficiency in infants, it is likely that these subjects will be hospitalized during the first several weeks on study. Page **50** of **76**

Continuation of this initial hospitalization for participation in the trial is not considered an SAE. Also, a hospitalization to accommodate a study procedure is not considered an SAE. However, during the hospitalization, AEs will be collected and assessed for seriousness & reported appropriately (e.g., important medical event or prolonged hospitalization).

All SAEs and IARs must be reported to the Sponsor as described in Section 7.4.

7.1.2 Laboratory Test Abnormality

Laboratory test results will be recorded on the laboratory page of the eCRF. Out of range laboratory test values will be reported as AEs (on the AE page of the eCRF) if they are considered to be clinically significant abnormalities by the Investigator and represent a change from the subject's baseline values.

7.2 Handling of Safety Parameters

7.2.1 Serious Adverse Events and Infusion-Associated Reactions(Immediately Reportable to the Sponsor)

All SAEs and IARs, irrespective of the treatment received by the subject, must be reported to the Sponsor or designee immediately and no later than 24 hours of the Investigator's first knowledge of the event (expedited reporting).

7.2.2 Adverse Event Reporting Period

The study period during which AEs must be reported is defined as the period from the signature of informed consent to the end of the study treatment follow-up. AEs occurring after signing the informed consent but prior to the first dose of study medication will only be recorded if assessed as related to protocol procedures or requirements. For this study, the study treatment follow-up is defined as a minimum of 30 days after the last dose of IMP. If a subject experiences an SAE that is considered to be related to study treatment at any time after the study, it must be reported to the Sponsor.

7.2.3 Treatment and Follow-up of Adverse Events

During the study, all AEs and SAEs will be followed up until they have returned to baseline status or stabilized or until the Investigator and Sponsor or designee agree that follow up is no longer necessary. If a clear explanation is established, it should be documented.

Treatment of AEs is at the discretion of the Investigator, and should follow the standards of medical care at the Investigator's institution.

7.2.4 Follow-up of Abnormal Laboratory Test Values

In the event of unexplained clinically significant abnormal laboratory values, the tests should be repeated and followed up until they have returned to baseline values and/or an adequate explanation of the abnormality is found. If a clear explanation is established, it should be documented.

Page 51 of 76

7.2.5 Pregnancy

Subjects in this study will be of non-reproductive potential.

7.3 Recording of Adverse Events

At each contact with the subject (and the subject's parent or legal guardian), the Investigator must seek information on AEs by specific questioning and, as appropriate, by examination. Information on all AEs should be recorded immediately in the source documentation, and in the eCRF. All clearly related signs, symptoms, and abnormal diagnostic procedures results should be recorded under one diagnosis.

AEs will be recorded from the time of signing of the informed consent until completion of the last scheduled visit, i.e., the follow-up visit. AEs occurring after signing the informed consent but prior to the first dose of study medication will only be recorded if assessed as related to protocol procedures or requirements. Any AEs remaining unresolved at the completion of the last scheduled visit should be recorded as ongoing. Ongoing AEs/SAEs should continue to be followed up for the period specified in Section 7.2.2 but without further recording in the eCRF. However, follow-up information on SAEs must be reported to the Sponsor or designee as described in Section 7.4.1. Any SAE that occurs after the study period and is considered to be related to the study treatment or study participation should be recorded and reported immediately.

Any AE that occurs within 24 hours of the infusion will be recorded by time and date, AEs occurring 24 hours after the infusion will be recorded by date only. The date and time, or the date when the AE started and stopped, as well as the intensity, seriousness, action taken with regard to the study treatment, causality assessment and outcome of the event will be recorded for each AE.

7.4 Reporting of Serious Adverse Events and Unanticipated Problems

Investigators and the Sponsor must conform to the AE reporting timelines, formats and requirements of the various entities to which they are responsible. (§13 GCP-V; Detailed guidance on the collection, verification and presentation of adverse event/reaction reports arising from clinical trials on medicinal products for human use ['CT-3']; US CFR Title 21, §312.32, Investigational New Drug [IND] safety reporting). The Sponsor or designee will report all reportable events to all regulatory authorities and Investigators as required by local regulations.

All SAEs, IARs, and other reportable events (see Section 7.4.3) must be reported to the Sponsor or designee in an expedited manner according to timelines described in Section 7.4.1.

Periodic Safety reporting to competent authorities will be done by the Sponsor according to national and local regulations.

7.4.1 Investigator Reporting: Notifying the Study Sponsor

Any SAE, IAR or unanticipated problem posing risk of harm to subjects, must be reported to the Sponsor, or designee immediately, and no later than 24 hours of the Investigator's first knowledge of the event. To report such events, a SAE/IAR form must be completed by the Investigator and sent to the study Sponsor or designee within 24 hours. The Investigator will keep a copy of this SAE or IAR form on file at the study site.

The Investigator must promptly provide further information on the SAE, IAR, or the unanticipated problem. This should include a copy of the completed SAE or IAR form, and any other diagnostic information that will assist the understanding of the event. Significant new information on ongoing SAEs or IARs must be reported to the Sponsor or designee immediately and no later than 24 hours of the Investigator's knowledge.

Report SAEs and IARs by phone, fax or email to:

For cases in North America	For cases in Europe							
Phone: PPD	Fax: PPD							
Fax:	Email: ^{PPD}							
Email ^{PPD}								

7.4.2 Investigator Reporting: Notifying the IRB/IEC

Unanticipated problems posing risks to subjects or others as noted above will be reported to the IRB/IEC according to local regulations. Copies of each report and documentation of IRB/IEC notification and acknowledgement of receipt will be kept in the Investigator's study file.

7.4.3 Sponsor Reporting: Notifying Regulatory Authorities

The study Sponsor is required to report certain study events in an expedited fashion to the Food and Drug Administration (FDA), the EMA and to all country Regulatory Authorities where the study is being conducted. The following describes the safety reporting requirements by timeline for reporting and associated type of event:

Immediately and within 7 calendar days

- Any suspected adverse reaction that is_associated with the use of the study drug, unexpected, and fatal or life threatening.
- Follow-up information must be reported in the following 8 days.

Immediately and within 15 calendar days

- Any suspected adverse reaction that is associated with the use of the study drug, unexpected, and serious, but not fatal or life threatening
- Any finding from tests in laboratory animals that_suggest a significant risk for human subjects including reports of mutagenicity, teratogenicity, or carcinogenicity.
- Any event in connection with the conduct of the study or the development of the IMP which may affect the safety of the trial subjects.

Page 53 of 76

• Follow-up information must be reported within 15 calendar days

The Sponsor will comply with all additional local safety requirements, as applicable. Periodic safety reporting to competent authorities will be done by the Sponsor or designee according to national and local regulations.

7.4.4 Sponsor Reporting: Notifying Participating Investigators

It is the responsibility of the study Sponsor to immediately notify all participating Investigators, in of any suspected AE associated with the use of the drug that is both serious and unexpected, as well as any finding from tests in laboratory animals that suggest a significant risk for human subjects.

7.5 Dose Modification and Stopping Rules

Upon a recommendation from the independent SC (see Section 7.6.1), the Sponsor may suspend dosing for an individual subject or all subjects enrolled in the study, at any time, due to poor tolerance or potential safety risks.

Specific rules for suspending dosing in an individual subject are provided in Appendix C.

7.6 Medical Monitoring

It is the responsibility of the Investigator to oversee the safety of the study at his/her site. This safety monitoring will include a thorough assessment and appropriate reporting of AEs as noted above, as well as the construction and implementation of a site data and safety-monitoring plan (see Section 10). Medical monitoring will include a regular assessment of the number and type of SAEs.

7.6.1 Independent Safety Committee

The oversight of the subject safety in the study will be provided by an independent Safety Committee. The activities and composition of the SC will be outlined in the SC Charter which will be ratified during the initial meeting, prior to commencement of dosing of the study subjects. The SC will be tasked with ongoing review of safety and efficacy data in order to advise the study Investigators regarding dose continuation and dose escalation decisions for the study (see Section 3.1 for details). The SC will be comprised of a group of individuals with pertinent medical expertise that reviews, on a regular basis, the conduct of this study and the emergent safety data. This SC will provide oversight and monitoring of the clinical study in compliance with GCP and associated guidance materials. These safety monitoring functions and the oversight of such activities are distinct from the requirement for study review and approval by an IRB or IEC.

The SC is an independent body of experts that serves in an advisory capacity to the Sponsor to ensure that clinical trial participants are not exposed to unreasonable or unnecessary risks. Collectively, the SC will have methodological and clinical expertise relevant to the study design and population. SC membership will begin before the start of the clinical trial and last for its duration.

Page 54 of 76

Core members of the SC will not participate in the trial as Investigators or sub-investigators, as members of any team otherwise participating in the trial, or in any other capacity that may compromise their privileged activities on the SC. Neither members of the SC nor their immediate families will have a direct financial interest in the Sponsor or an interest that is dependent on the outcome of the trial. To be considered for SC membership, all candidates must disclose all actual or potential conflicts of interest, including any financial interests in, or research activity on a competing product. SC members will be compensated at an appropriate market rate for time spent reviewing, discussing, and attending the meetings. The Sponsor will also reimburse SC members for any out-of-pocket travel expenses required for attendance at the meetings. Aside from the above, SC members will receive no additional compensation for their membership on the committee.

Page 55 of 76

8 Statistical Plan

The Sponsor or its designee will be responsible for data collection and editing, reviewing and validating all the information in the eCRFs, statistical analysis, and generation of the clinical study reports.

The primary analysis and all planned secondary and exploratory analyses will be performed after all subjects have reached 12 months of age or have died or withdrawn from the study. All formal statistical conclusions will be drawn based on these analyses.

Final analyses will also be performed after all subjects have completed treatment in the study (up to 5 years) or have died or withdrawn from the study. These analyses will be considered supportive rather than confirmatory.

Prior to locking the database for each of the above-mentioned analyses, all data editing will be complete and decisions regarding the evaluability of all subject data for inclusion in the statistical analysis will be made. The rationale for excluding any data from the statistical analyses will be prospectively defined, and classification of all or part of a subject's data as non-evaluable will be completed and documented before the entire database is locked.

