8.1 General Considerations

All data will be presented in listings, and summary tables and/or graphs will be provided, as appropriate. Unless otherwise noted, all tabulations for efficacy endpoints will be presented for subjects in the Primary Efficacy Analysis Set and tabulations for other endpoints will be presented for subjects in the Full Analysis Set (FAS). Descriptive summary statistics (n, mean, median, standard deviation, minimum and maximum) will be calculated for the continuous variables. Shift tables and/or frequencies and percentages will be produced for the categorical variables. When percentages are reported, the number of treated subjects will be used as the denominator. As noted, 95% two-sided confidence intervals (CIs) will be calculated around the estimates based on the exact binomial distribution for binomial endpoints and the t-distribution for continuous endpoints.

Baseline will be defined as the last measurement prior to the first infusion of sebelipase alfa. (Note: For exploratory analyses, the first available measurement after initiation of treatment may be used as baseline if a pretreatment measurement is unavailable.) Survival rates will be based on the age of the subject. Other endpoints, unless otherwise noted, will be based on exposure (i.e., duration of time since the first infusion of sebelipase alfa).

Details of the planned analyses and statistical methodologies will be provided in a separate Statistical Analysis Plan (SAP).

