8.7 Efficacy Analysis

Efficacy will be analyzed for the Primary Efficacy Analysis Set. If the PPS is not identical to the Primary Efficacy Analysis Set (i.e., if at least one patient in the Primary Efficacy Analysis Set is excluded from the PPS), efficacy analyses will be repeated for the PPS.

The primary efficacy endpoint is the proportion of subjects surviving to 12 months of age. It is not anticipated that any subjects will be lost to follow-up prior to 12 months of age, but a subject who is not confirmed to have survived to 12 months of age will not be considered to have met the primary endpoint. As a complementary analysis, Kaplan-Meier survival curves of survival since birth and survival since first dose of IMP will be presented.

Survival at 18 and 24 months of age will be analyzed as described for the primary endpoint. Median age at death will also be calculated. A Kaplan-Meier estimate of median survival past first dose of IMP will be computed.

Estimated survival rates and median age at death derived from this study will be compared to rates/times reported in the literature, and will be discussed in conjunction with information derived from a natural history study in a similar patient population (study LAL-1-NH01).

Anthropometric indicators of growth, standardized by age and gender in accordance with the methodology described by the WHO and using WHO growth charts will be listed by study time point as observed values and as changes from baseline. Change from baseline in anthropometric data will be tabulated as continuous data. In addition, the percentages of subjects who meet criteria for underweight, stunting, and wasting will be tabulated for each timepoint. For anthropometric indicators of growth, age will be adjusted for prematurity if gestational age is <37 weeks and the subject is under 12 months of age. The adjustment will be made such that corrected age = chronological age minus the number of months premature.

Change and/or percent changes from baseline in AST, ALT, and serum ferritin will be tabulated for each evaluation timepoint.

A subject will be considered to have achieved transfusion-free hemoglobin normalization (TFHN) if the subject meets all of the following criteria:

- 1. Has two post-baseline measurements of hemoglobin at least 4 weeks apart that are both above the age-adjusted lower limit of normal (LLN);

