7. GENERAL ISSUES FOR STATISTICAL ANALYSIS

7.1 General Statistical Methodology

All data will be presented in patient data listings. Descriptive summaries and/or graphics will be provided where appropriate for each of the analysis variables.

Continuous quantitative variable summaries will include the number of subjects (n) with non-missing values, mean, standard deviation, minimum, first quartile (Q1), median, third quartile (Q3), and maximum.

Shift tables and/or frequencies and percentages will be produced for categorical variables. In general, the denominator for the percentage calculation will be based upon the total number of subjects in the study population for the group, unless otherwise specified.

Listings with the potential for multiple timepoints per topic (eg, labs) will have Dosing Regimen at Time of Xxxx. Dosing Regimen at Time of the assessment/event/etc will be the dose that preceded the assessment (ie, not necessarily the dose given on the day of the assessment). Vital Signs and AEs/IRRs occurring during or following an infusion should have the dose associated with the infusion – ie, the dose administered during the infusion.

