7.1.1 Handling of Missing Data

All data will be analyzed as they were collected in the database. Missing data will not be imputed.

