9.1 Efficacy Endpoint Analysis

The primary endpoint is the proportion of subjects surviving to 12 months of age. A 95% exact confidence interval, calculated using the Clopper-Pearson method [Clopper and Pearson, 1934], will also be presented.

It is not anticipated that subjects will be lost to follow-up prior to 12 months of age; however, subjects in the PES who are not confirmed to have survived to 12 months of age will not be considered to have met the primary endpoint. As a complementary analysis, Kaplan-Meier survival curves of survival since birth and survival since first dose of SBC-102 will be presented. A Kaplan-Meier estimate, with 95% CI if appropriate, of median survival post first dose of SBC-102 will also be provided.

The proportion of subjects surviving to 18 and 24 months of age will also be analyzed as described for the primary endpoint (i.e., percent of subjects in the PES surviving to 18 and 24 months). These proportions will also be estimated by Kaplan-Meier (product-

limit) methodology if there are subjects whose survival times are censored prior to 18 or 24 months.

The median age at death will be calculated and presented in a summary table. The median will also be estimated by Kaplan-Meier (product-limit) methodology.

Estimated survival rates and median age at death derived from these analyses will be compared to rates/times reported in the literature, and will be discussed in conjunction with information derived from the natural history study in a similar patient population (study LAL-1-NH01). Further, a separate Kaplan-Meier survival curve for survival from birth will be constructed for the patient population in LAL-1-NH01.

Anthropometric indicators of growth, standardized by age and gender in accordance with the methodology described by the WHO and using WHO growth charts will be listed by study time point as observed values and as changes from baseline. Change from baseline in anthropometric data will be tabulated as continuous data. In addition, the percentages of subjects who meet criteria for underweight (<-2 standard deviations [SD] from the median for WFA), stunting (<-2 SD from the median for LFA/HFA), and wasting(<-2 SD from the median for WFL/WFH) will be tabulated for each timepoint.

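### At the 12-months-of-age analysis, the PES percent for 18- and 24-month survival counts living children who are still too young as non-survivors, and the stated data scope does not fit that schedule

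*Protocol*

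**What the plan says.** **Timing.** The opening of Protocol section 8 sets the trigger: "The primary analysis and all planned secondary and exploratory analyses will be performed after all subjects have reached 12 months of age" (death or withdrawal also counts). It adds: "All formal statistical conclusions will be drawn based on these analyses". The later end-of-study analyses are classed as supportive. Survival at 18 and 24 months of age is a listed secondary endpoint (Protocol 3.2.2.1, SAP 2.2.2).

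**Method.** Protocol 8.7: "Survival at 18 and 24 months of age will be analyzed as described for the primary endpoint". SAP 9.1 says the same and spells it out as "percent of subjects in the PES surviving to 18 and 24 months". Under the primary endpoint's rule, a child whose survival to the age is not confirmed has not met the endpoint.

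**Second estimate.** SAP 9.1 continues: "These proportions will also be estimated by Kaplan-Meier", on condition that some survival times are censored before 18 or 24 months.

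**Data scope.** The synopsis (statistical plan) and Protocol section 12 describe the report tied to the 12-month endpoint as holding each subject's data up to 12 months of age, death or early withdrawal. SAP 4.2 speaks only of the final study report and gives no data cut.

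**General rules.** Protocol 8.1: "When percentages are reported, the number of treated subjects will be used as the denominator". SAP 7.1, as a general rule that yields to anything more specific: "the denominator for the percentage calculation will be based upon the total number of subjects in the study population for the group". SAP 7.1.1: "Missing data will not be imputed".

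**The concern.** The trigger guarantees that every surviving child has turned one. It does not guarantee that any has turned 18 or 24 months. A child alive at 13 months of age when the analysis is run cannot be confirmed as surviving to 18 months, yet stays in the PES. The planned percent then partly measures how old the children are at the cut and not how long they live.

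Separately, section 8 asks for 18- and 24-month results at an analysis whose report is described elsewhere as stopping at 12 months of age. A statistician following both instructions would have nothing to analyse at the later ages.

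At stake is how the secondary survival results read in the report from which the formal conclusions are to be drawn: a treatment under which no child dies after the first birthday could show an apparent fall in survival between 12 and 18 months.

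**Working it through.** **Inputs.** PES of 8 with 6 survivors to 12 months, and the 1/18 natural-history result (Protocol 8.2, SAP 5); exact Clopper-Pearson 95% intervals (SAP 9.1). Assumed: two deaths at separate ages before 12 months, no later deaths, no earlier censoring, and k of the 6 living children younger than the target age at the cut. The documents give no birth or enrolment dates, so k is shown as a range.

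**The plan's own figures.** Clopper-Pearson gives 34.91-96.81% for 6/8 and 0.14-27.29% for 1/18. Both match the documents.

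**Reading A: follow-up beyond 12 months of age is in the analysis.** The PES percent is (6 − k)/8, so each child still too young costs 1/8 = 12.5 percentage points.

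| k too young | PES percent | Exact 95% CI | Kaplan-Meier | Followed to that age |
|---|---|---|---|---|
| 0 | 6/8 = 75.0% | 34.91-96.81% | 75% | 6 |
| 1 | 5/8 = 62.5% | 24.49-91.48% | 75% | 5 |
| 3 (assumed) | 3/8 = 37.5% | 8.52-75.51% | 75% | 3 |
| 5 (assumed) | 1/8 = 12.5% | 0.32-52.65% | 75% | 1 |

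Kaplan-Meier from birth is (7/8) × (6/7) = 75% in every row, because the children too young are censored after both deaths. The Greenwood sum is 1/(8×7) + 1/(7×6) = 1/56 + 1/42 = 0.04167, and a log-log 95% interval is 31.5-93.1%. The interval method is an assumption, as the SAP names none.

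Dropping only the living children who are too young does not repair the percent, since the deaths all stay in: (6 − k)/(8 − k) is 5/7 = 71.4% (29.04-96.33%) for k = 1 and 3/5 = 60.0% (14.66-94.73%) for k = 3.

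**How large might k be?** As illustration only, take 8 births evenly spaced, all children alive, and the cut at the youngest child's first birthday. Ages at the cut are 12, 12 + g, …, 12 + 7g months for spacing g.
- g = 2 months: 5/8 have reached 18 months and 2/8 have reached 24.
- g = 6 months: 7/8 and 6/8.

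True survival in both cases is 100%. In general k is zero if the cut falls at least 6 months (for 18) or 12 months (for 24) after the first birthday of the youngest living PES child. Section 8 neither requires nor forbids such a lag.

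**Reading B: data stop at 12 months of age, as the synopsis and section 12 read literally.** All 6 survivors are censored at 12 months. The PES percent at 18 and 24 months is 0/8 (exact 95% CI 0-36.94%) whatever the children's real ages. Kaplan-Meier is 75% at 12 months, but nobody is followed beyond that, so it is not estimable at 18 or 24 months.

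Readings A and B are alternatives. The table does not apply under B, and the 0/8 does not arise from truncation under A.

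**The case against.** The strongest reply is that SAP 9.1 already deals with the case. A living child below the target age is exactly the censoring that triggers the Kaplan-Meier estimate, and Protocol 8.1 leaves methodological detail to the SAP. This stands: if follow-up past 12 months of age is included, a sound estimate will be in the report. What remains is that it appears beside a leading percent that can be badly low, and that the stated data scope may remove the follow-up it needs.

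A reader might infer that the plan leaves open which of the two estimates is the main one. It does not: SAP 9.1 puts the PES percent first and adds Kaplan-Meier. The difficulty is that this order leads with the percent, which is the wrong one of the two for that cut.

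A reader might also infer that the general denominator rules compel the result. They are weaker support than they look. Protocol 8.1 refers to treated subjects, which describes the Full Analysis Set, and SAP 7.1 is expressly a default. The finding rests on SAP 9.1's own PES wording and the carried-over rule for unconfirmed survival. Nothing elsewhere overrides these: not imputing missing data does not take a child out of the denominator, the pre-lock evaluability decisions in Protocol section 8 state no rule for these children, and the 'as data permit' qualifier in Protocol 3.2.2.1 sets no denominator.

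Literal truncation at 12 months of age would make section 8's own schedule pointless, so it may not be intended. That is fair, and it is why the passages need reconciling.

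The consequences are also limited. No formal hypothesis tests are planned (Protocol 8.11.1), data are listed by subject so that with about 8 children a reader can see who was simply too young, and the final analysis, after up to 5 years of treatment, should not have the problem to any material extent.

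**Conclusion.** The point holds as a mismatch between schedule, data scope and estimator at the first report; minor to moderate priority. Followed as written, the plan gives either a percent that falls by 12.5 points for each living child still too young (5/8 with one, 3/8 with an assumed three, against 6/8) or, if data stop at 12 months of age, 0/8 with no usable Kaplan-Meier estimate. These figures rest on the plan's 6/8 scenario with no later deaths. The real number of children too young depends on dates not in the documents and may be zero.

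The bias runs against the treatment, the results are descriptive, and the effect is confined to the earlier report. The 12-month primary endpoint is unaffected. One might be tempted to note that 5/8 has a lower limit of 24.49%, below the 27.29% natural-history upper limit, and conclude that the efficacy case could fail. The documents do not support that: Protocol 8.2 and SAP 5 set that benchmark for 12-month survival only, and no decision rule attaches to 18 or 24 months.

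**What to change.** Keep the trigger in Protocol section 8, and make two changes.

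1. In the synopsis, Protocol section 12 and SAP 4.2, state that survival follow-up for all subjects up to one named data-cut date enters the analysis run at that trigger.
2. In SAP 9.1, make the already planned Kaplan-Meier estimate, with the number at risk, the estimate of 18- and 24-month survival at that cut, and report 'not estimable' if no child has been followed to the age. Give the simple PES percent only once every PES subject has died or would, by date of birth, have reached that age. Do not substitute a percent that drops only the living children who are too young.

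Cost: a few sentences and no new data collection, since follow-up already continues beyond 12 months of age. Survival data beyond 12 months of age must, however, be cleaned for the first report, the simple 18- and 24-month proportions come later than now scheduled, and the early Kaplan-Meier estimates will rest on few children.
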